#### STATISTICAL ANALYSIS PLAN

# Sample size calculation

Using a repeated measurements analysis of variance model for the primary endpoint with 4 time-points, a sample size of 111 patients will have a power=80% at a significance level of 5% to detect small effect size in term of f (f=0.10) assuming a correlation among repeated measures of 0.6.

### Statistical analysis

Descriptive analyses of patients' characteristics will be provided. For continuous variables, the mean and standard deviation (SD) or the median and interquartile range (IQR) will be calculated as appropriate. The normality assumption about the distribution of continuous variables will be tested using the Kolmogorov-Smirnov test. Categorical variables will be summarized with frequencies absolute counts and percentages. Repeated measures ANOVA will be implemented to assess temporal trend in quantitative variables while dichotomous items will be analyzed using a mixed-effect generalized linear model. All statistical analysis will be performed using R software (www.r-project.org).

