### Inclusion criteria

- 1. Age  $\geq$  18 years.
- 2. Pre-menopausal status.
- 3. Ultrasound diagnosis of benign myometrial lesion.
- 4. Symptomatic patients presenting with abnormal uterine bleeding (menorrhagia/metrorrhagia).
- 5. Availability of ultrasound images in digital format.
- 6. Signature of Informed Consent

It is Specified that patients with a clinical indication for surgery may be included in the study if symptomatic for abnormal uterine bleeding.

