# Variables and procedures

All women enrolled in the study will sign an informed consent form.

Patients retrospectively identified from the institutional registry may be included in the protocol if clinical data and ultrasound examinations are available, prior written consent. Recorded data will be retrieved from the examinations at baseline (before treatment) and 3 months, 6 months, and 12 months after treatment initiation.

Patients enrolled prospectively will be managed according to the activities and procedures depicted in Table 1. Clinical and ultrasound data will be recorded at baseline (before treatment) and 3 months, 6 months, and 12 months after treatment initiation.

Study data will be collected according to a dedicated eCRF that includes clinical, ultrasound, and pathological information (Appendix 1 MySaturn study).

The eCRF will be implemented using RED Cap platform (ref: https://projectredcap.org)

Study data will be collected and managed using REDCap electronic data capture tools hosted at Fondazione Policlinico Universitario A. Gemelli, IRCCS (https://redcap-irccs.policlinicogemelli.it/). REDCap (Research Electronic Data Capture) is a secure, web-based application designed to support data capture for research studies, providing 1) an intuitive interface for validated data entry; 2) audit trails for tracking data manipulation and export procedures; 3) automated export procedures for seamless data downloads to common statistical packages; and 4) procedures for importing data from external sources. People officially registered as study investigators or data managers will receive a user login to access the REDCap web platform and enter/manage data.

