#### **ENDPOINTS**

# Primary endpoint

Modifications in the volume of the index myometrial lesion during treatment with relugolix/estradiol/norethisterone;

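### Repeated-measures ANOVA for lesion volume usually drops women without all four scans; a linear mixed model on every available scan is a cheap improvement

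*Protocol*

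**What the plan says.** The primary endpoint is "Modifications in the volume of the index myometrial lesion during treatment with relugolix/estradiol/norethisterone". Under Statistical analysis the protocol fixes the method: "Repeated measures ANOVA will be implemented to assess temporal trend in quantitative variables". In the same sentence, dichotomous items go to a generalized linear mixed model, which can use incomplete series.

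The sample size rests on the same method: "Using a repeated measurements analysis of variance model for the primary endpoint with 4 time-points", where "a sample size of 111 patients will have a power=80% at a significance level of 5" per cent, for f = 0.10 and "assuming a correlation among repeated measures of 0.6".

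On who contributes scans, Variables and procedures schedules prospective women at baseline, 3, 6 and 12 months. Retrospective women "may be included in the protocol if clinical data and ultrasound examinations are available", and "Recorded data will be retrieved from the examinations at baseline (before treatment) and 3 months, 6 months, and 12 months after treatment initiation". The Inclusion criteria add that "patients with a clinical indication for surgery may be included in the study if symptomatic for abnormal uterine bleeding".

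**The concern.** Classical repeated-measures ANOVA needs a value at every visit, so a woman who misses one scan drops out of the analysis of the primary endpoint. The binary secondary features, in contrast, get a method that keeps her.

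Gaps are foreseeable among prospective women, who must return three times over a year. Some may have surgery, since an indication for it does not bar entry, and leaving may be related to how the lesion responds. The study's main product is an estimate of volume change in a single uncontrolled cohort, so there is no comparison group in which such a bias could cancel. Extra patients would not remove it.

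**Working it through.** **1. The plan's own figure.** Inputs from Sample size calculation: f = 0.10, m = 4 time points, correlation 0.6, alpha 5%. For one group, with sphericity:

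- noncentrality λ = f² × N × m / (1 − ρ) = 0.01 × N × 4 / 0.4 = 0.1 × N
- degrees of freedom 3 and 3(N − 1)
- N = 110: λ = 11.0, power 79.9%
- N = 111: λ = 11.1, df 3 and 330, power 80.3%

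So 111 is reproduced exactly, as the smallest number of complete four-scan series that reaches 80%.

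**2. Bias if loss follows observed response.** The documents give no loss rates, SDs or trajectories, so all of these are assumptions: 111 women, log volume, baseline SD 0.9, response SD 0.35, measurement SD 0.15, true 12-month reduction 25%, and a logistic leaving model with slope 1 per SD of the observed response. Estimated 12-month reduction at 10/20/30% loss, from simulation:

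| Who leaves | Complete cases | Mixed model, random intercept | Mixed model, unstructured |
|---|---|---|---|
| Poor observed responders | 27/29/31% | 26/27/28% | 25/25/25% |
| Good observed responders | 23/20/18% | 24/23/22% | 25/25/25% |
| At random | about 25% | about 25% | about 25% |

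The complete-case entry for good responders at 20% loss is 20 or 21%, depending on the assumed trajectory. A random intercept removes only about half of the bias: at 30% loss of poor responders the error falls from 31 − 25 = 6 points to 28 − 25 = 3.

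If leaving depends on the unseen 12-month value, every method is biased, the unstructured model least. When poor responders leave, it gives 26/26–27/27%, against 28/30/32% for complete cases.

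On raw volume, with a true mean reduction of 20.3%, complete cases give 23/25/27% or 18/16/13% and the unstructured model 20.1–20.4%. The result therefore does not depend on the log scale.

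**3. Power, as a separate scenario** (f = 0.10, equal correlation 0.6).

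- ANOVA on 99/88/77 complete series (111 less 10/20/30%, rounded down): λ = 9.9/8.8/7.7, power 75.0/69.3/62.7%.
- Unstructured mixed model, complete data: λ = 11.1 with df 3 and 108 gives 79.2% at 111. N = 113 (λ = 11.3, df 3 and 110) gives 80.0%.
- Unstructured mixed model, 12-month scan missing at random in 10/20/30% of 111 women: 76–79/72–78/67–78%, depending on the shape of the trend.

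**4. Power if correlation decays with time** (assumed 0.9196 to the power of months, mean 0.6, epsilon about 0.75), 111 complete series:

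- Linear trends: unstructured model 53–56%, Greenhouse-Geisser ANOVA 67%.
- Early plateau: 88% against 74%.
- With 10/20/30% loss, trend linear in months: 51/48/46% against 61/57/51% for complete-case Greenhouse-Geisser.
- With the same loss, early plateau: 88/88/88% against 68/61/55%.

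**5. Steps 2 and 3 describe different settings.** The SDs in step 2 imply a baseline-to-12-month correlation of 0.81 / √(0.8325 × 0.955) = 0.91, where 0.81 = 0.9², 0.8325 = 0.9² + 0.15² and 0.955 = 0.9² + 0.35² + 0.15². The mean over all visit pairs is about 0.95, not 0.6. In that setting a 25% reduction is detected with near certainty by either method, even with 77 complete series.

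**The case against.** **The complete-case rule is not written down.** The protocol names a method, R routines differ in how they treat incomplete series, and such handling often sits in a separate SAP. That stands as far as it goes: a reader might infer that the protocol prescribes complete-case analysis, and it does not say so. But it does fix ANOVA for quantitative variables and names a mixed model only for the dichotomous ones. The point challenges that stated choice; it does not ask for missing detail.

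**Missing scans are not shown.** This also stands. No loss rate is given, and an indication for surgery need not mean surgery within 12 months. The digital-image criteria (inclusion 5, exclusion 9) and the retrieval sentence can be read as requiring all scans of retrospective women, who would then add no gaps, though they would be selected for completeness. The point therefore rests on the prospective women.

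**The sample size paragraph is right.** It is, and four time points already imply four scans. A reader might infer that 111 is wrong or that the study is underpowered; neither follows.

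**The mixed model is not better in every respect.** Correct. If correlation decays with time, the unstructured model loses power for linear trends, and temporal trend is the stated purpose of the analysis. The covariance choice is a genuine trade-off. The case for the change is bias under response-related loss, not sphericity or restored power.

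**Conclusion.** The point holds as a cheap improvement in method. ANOVA in its usual form would bias the estimated volume change if loss depends on observed response. Under the assumptions used, the error is about 2 percentage points at 10% loss and 6 to 7 points at 30%, around a true 25%. A mixed model on all scans with unstructured covariance removes it under missing at random, reduces it if leaving depends on unseen values, and changes nothing under random loss.

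Three stronger readings are not supported:

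- That shrinkage will be overstated. The direction depends on who leaves, and the documents do not show that.
- That bias and loss of power occur together. The bias figures imply a mean correlation of about 0.95 and the power figures use 0.6, so they are separate scenarios.
- That the mixed model restores 80% power. With incomplete series it recovers only part of what is lost.

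The weakness of the method is clear; the rate and direction of loss are unknown, so confidence in the practical effect is medium.

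**What to change.** **Statistical analysis.** Replace repeated-measures ANOVA for lesion volume and the other quantitative endpoints with a linear mixed model, visit as a factor, using every available scan of every woman with a baseline. Prespecify the covariance; unstructured is suggested, because a random intercept left about half of the bias. State the missing-at-random assumption and acknowledge the lower power for linear trends if correlation decays with time. If ANOVA is kept, say how incomplete series are handled and apply a Greenhouse-Geisser correction.

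**Sample size calculation.** No correction is needed for the ANOVA. If the mixed model is adopted, give its own power: about 79% for 111 complete series, and lower with incomplete ones.

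**Cost.** Wording in two paragraphs and standard routines in R, which the protocol already names. More patients are optional: 2 more (113) would reach 80% with complete series under the mixed model. The statistical price is reliance on missing at random and the loss of power shown above.

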#### **SAFETY**

### **Definitions**

Adverse event: any untoward medical occurrence in a patient administered a medicinal product and which does not necessarily have to have a causal relationship with this treatment. Adverse reaction: a response to a medicinal product which is noxious and unintended. Adverse reactions may arise from use of the product within or outside the terms of the marketing authorisation or from occupational exposure. Use outside the marketing authorisation includes off-label use, overdose, misuse, abuse and medication errors.

Serious adverse reaction: any untoward medical occurrence that at any dose results in death, is life-threatening, requires inpatient hospitalisation or prolongation of existing hospitalisation, results in persistent or significant disability or incapacity, or is a congenital anomaly/birth defect or represents a new important medical event.

### Regulatory management of adverse events

Any adverse event will be collected, recorded and assessed for seriousness and relatedness with study drug(s) or any other medicinal products in use, in order to identify suspected adverse reactions (ADRs).

All ADRs, regardless of the seriousness and expectedness, will be reported to National Competent Authority - AIFA, via the National Pharmacovigilance Network through the figure of Local Pharmacovigilance Responsible, as requested by the applicable law for the post-marketing pharmacovigilance activities (DM 30.04.2015 and GVP, module VI) and to the EC per local applicable rules. For the retrospective study with secondary analysis of clinical data, there is no further need of ADR reporting to national Competent Authority - AIFA, since all the reporting obligations have been fulfilled at the time of ADR presentation (DM 30.04.2015 and GVP module VI, section C 1.2.1.2.).

### ETHICAL CONSIDERATIONS

Prior to initiation of a study site, the Sponsor will obtain approval from Ethics Committee to conduct the study in accordance with regulatory requirements. The study will be conducted in accordance with Good Clinical Practice (GCP), all applicable subject privacy requirements, and the guiding principles of the declaration of Helsinki.

# **Informed Consent**

Patients eligible for this study will be required to sign the Informed Consent Form in the context of a follow-up outpatient visit in which a study collaborator should be present. It will also be necessary to be able to use the data of patients who did not give Informed Consent because they are deceased, as failure to include this population would reduce the sample size producing negative consequences for the study in terms of significance of the results.

A copy of the written consent signed by the patient will be kept by the center in the appropriate section of the trial site file.

# **Confidentiality**

Information about study participants will be kept confidential and managed under the applicable laws and regulations.

The investigator must ensure pseudonymized of the patients. Patients must not be identified by names in any documents submitted to the study promoter. Patient enrolment log must be kept strictly confidential to enable patient identification at the site

The investigator/institution should take measures to prevent accidental or premature destruction of these documents. Essential documents should be retained for a period of not less than seven years from the completion of the Clinical Trial.

# Sponsorship and financing

The study is spontaneous, not sponsored by pharmaceutical companies.

### Insurance

Given the observational nature of the study, no insurance policy will be necessary.

